5 SAFETY REPORTING

5.1 DEFINITIONS OF ADVERSE EVENTS

Adverse Event (AE): any untoward medical occurrence in a patient or clinical study participant.

Serious Adverse Event (SAE): any untoward and unexpected medical occurrence or effect that:

- Results in death
- **Is life-threatening** refers to an event in which the participant was at risk of death at the time of the event; it does not refer to an event which hypothetically might have caused death if it were more severe
- Requires hospitalisation, or prolongation of existing inpatients' hospitalisation
- Results in persistent or significant disability or incapacity
- Is a congenital anomaly or birth defect

Medical judgement should be exercised in deciding whether an AE is serious in other situations. Important AEs that are not immediately life-threatening or do not result in death or hospitalisation but may jeopardise the participant or may require intervention to prevent one of the other outcomes listed in the definition above, should also be considered serious.

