2.2 SECONDARY OBJECTIVES

- 1. To identify factors that determine the decision to use thrombectomy within the PERT team
- 2. To evaluate the factors that predict outcome of CAVT
- 3. To evaluate the patient tolerance and experience in the form of patient related outcome measures (PROMS) of CAVT

- 4. To evaluate the effectiveness and risk profile of CAVT in high-risk patients, including effects of concurrent lytic therapy where given
- 5. To evaluate the effect of service design on PE CAVT rate and outcomes
- 6. To compare variability in provision of CAVT between hospitals and its effect on performance and outcomes.
- 7. To evaluate the relationship between severity and outcome in patients receiving CAVT
- 8. To determine imaging features that are associated with poor outcomes in patients undergoing CAVT
- 9. To determine the effectiveness of CAVT in relationship to the age of the thrombus
- 10. To evaluate the perceived dyspnoea at 30 days and 6 months after CAVT, and also in comparison to the non-intervened group
- 11. To evaluate Quality of life as assessed by EQ-5D-5L and PEmb-QoL at 30, 90 days and 6 months for all participants.
- 12. Incidence of device related SAE(s)
- 13. Evaluate the impact of the length of procedure time and the operator decided end point of CAVT, including technical success and its effect on outcomes
- 14. To evaluate the time to CAVT and its effect on outcomes and resource utilisation.

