5.2 REPORTING PROCEDURES

At each data collection (30 days, 90 days and 6 months from the thrombectomy) the investigator will determine whether adverse events about the device and procedure have occurred. Subjects participating in the study should be encouraged to report these AEs spontaneously or in response to general, non-directed questioning.

Relevant events will be collected from the signing of informed consent to the completion of the follow up 6 months post index procedure.

19/10/25; V1.0

Adverse Events

AEs will be recorded for the CAVT and relevant procedure only.

Any AEs related to the CAVT will also be reported to the company Penumbra and MHRA.

Please find in Appendix 3 expected adverse events of CAVT and relevant procedure.

Serious Adverse Events

Death due to any pre-existing conditions will not be reported as SAEs.

Serious adverse events will be recorded.

Only CAVT related SAEs will be reported to the Principle Investigator, the Chief Investigator and Sponsor within 24 hours of being aware of the event. An Independent Medical Reviewer for the SAEs will also be appointed and the opinion will be recorded along with the PI / CI opinion. A SAE form should be completed.

All CAVT related SAEs should be reported to the Name of REC and copied to the Sponsor, and Penumbra where in the opinion of the Chief / Principal Investigator and the Independent Medical Reviewer, the event was:

- 'related', i.e. resulted from the administration of any of the research procedures; and
- 'unexpected', i.e. an event that is not listed in the protocol as an expected occurrence

Reports of related and unexpected SAEs should be submitted within 15 days of the Chief / Principal Investigator becoming aware of the event, using the Non-CTIMP safety report to REC form for non-IMP studies.

Sponsor contact details for reporting SAEs

Please send SAE forms to: R&D Governance / R&D Office

[contact] (Mon to Fri 09.00 – 17.00)

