12.4 APPENDIX 4 – EXPECTED SERIOUS ADVERSE EVENTS

- acute vessel occlusion
- air embolism
- allergic reaction and anaphylaxis from contrast media or device material
- arrhythmia
- arteriovenous fistula
- cardiac injury, cardiac perforation, cardiac tamponade
- cardio-respiratory arrest
- compartment syndrome
- death
- emboli
- foreign body embolization
- haemorrhage
- infarction leading to organ damage
- · myocardial infarction
- neurological deficits including stroke
- pneumothorax
- · valvular damage

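### Section 5.1 builds unexpectedness into the SAE definition, which conflicts with Appendix 4 and section 5.2 and may lead sites to leave listed events out of the device-SAE count

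*Protocol*

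**What the plan says.** - **Protocol 5.1, adverse event (AE):** "any untoward medical occurrence in a patient or clinical study participant". Expectedness plays no part.
- **Protocol 5.1, SAE:** "any untoward and unexpected medical occurrence or effect that" meets a criterion such as death, threat to life, hospitalisation or lasting disability. This is the only SAE definition in the protocol. A closing paragraph adds that important AEs falling short of those outcomes, but endangering the participant or needing intervention to prevent one of them, "should also be considered serious". Expectedness is not mentioned there.
- **Protocol 5.2, recording:** "Serious adverse events will be recorded". CAVT-related SAEs go to the principal investigator, chief investigator and sponsor within 24 hours, with an SAE form and the recorded opinion of an independent medical reviewer.
- **Protocol 5.2, REC reporting:** CAVT-related SAEs go to the REC if they are both related and unexpected. Unexpected is explained as "an event that is not listed in the protocol as an expected occurrence".
- **Protocol 5.2, deaths:** "Death due to any pre-existing conditions will not be reported as SAEs".
- **Protocol Appendix 4:** 17 bullets under the title "EXPECTED SERIOUS ADVERSE EVENTS".
- **Protocol 2.2, secondary objective 12:** the incidence of device-related SAEs.

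**The concern.** Seriousness and expectedness are separate attributes of an event. Seriousness decides whether the event is an SAE; expectedness decides whether an SAE needs expedited reporting. Section 5.1 merges them. If the 5.2 meaning of unexpected is carried into 5.1, an event that is both serious and listed cannot be an SAE, although Appendix 4 calls it one.

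Three things are at stake:
- The numerator of secondary objective 12 depends on which text a site follows, and following 5.1 literally can only lower it.
- Twelve sites (section 1.4) could classify the same procedural stroke differently, which would also disturb comparisons between hospitals.
- The 24-hour notification, the SAE form and the independent medical review apply to SAEs only, so a listed event not classed as an SAE would miss them.

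A later analysis plan cannot reliably repair this. Sites classify events as they occur, working from the protocol, and an event never entered on an SAE form has no independent opinion on file.

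**Working it through.** The protocol states no SAE rate, so there is no figure to reproduce. The check sets the texts side by side.

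**Step 1. Does the definition require unexpectedness?** Yes. The AE and SAE definitions stand together in 5.1, and only the SAE definition carries the term.

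**Step 2. What does unexpected mean?** The only explanation is in 5.2, within the REC-reporting test: the event is not on the protocol's lists.

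**Step 3. What is listed?** Appendix 4 has 17 bullets: acute vessel occlusion; air embolism; allergic reaction and anaphylaxis; arrhythmia; arteriovenous fistula; cardiac injury, perforation or tamponade; cardio-respiratory arrest; compartment syndrome; death; emboli; foreign body embolisation; haemorrhage; infarction with organ damage; myocardial infarction; neurological deficits including stroke; pneumothorax; valvular damage. Appendix 3 also lists, as expected AEs, some events that could meet a seriousness criterion, such as emergent surgery, acute renal failure from contrast, and vessel perforation.

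**Step 4. Combine steps 1 to 3.** Under the main 5.1 definition, read with the 5.2 meaning, 0 of the 17 categories can be an SAE. Without the unexpectedness condition, all 17 can be, whenever a seriousness criterion is met.

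**Step 5. Do other parts of the protocol agree with the literal reading?** No.
- Appendix 4 itself calls the events serious adverse events.
- Section 5.2 applies unexpectedness to SAEs as a filter for the REC. That filter would be redundant if every SAE were already unexpected.
- The medical-judgement paragraph in 5.1 admits some events as serious with no expectedness condition. It covers events short of the main criteria, though. A milder listed event could therefore enter by this route while a life-threatening listed event fails the main definition.

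**Step 6. What is recorded whatever the SAE label?**
- Section 7.2 and Appendix 1 collect mortality at discharge, 30 days, 90 days and 6 months.
- Section 5.2 has AEs of CAVT and its procedure recorded, and CAVT-related AEs reported to the manufacturer and the MHRA.

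What may be lost is therefore the SAE classification and the handling that follows from it, not the event.

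**Step 7. Illustration only.** Assumptions not in the documents: every site follows the literal reading, the medical-judgement route is not used, the true device-SAE incidence is 2% to 10%, and 50% to 100% of those events are listed. The planned number of thrombectomy patients is 200 (study summary). Patients counted = 200 × true rate × (1 − share listed).

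| True rate | Patients with an SAE | Counted, 50% listed | Counted, 100% listed |
|---|---|---|---|
| 2% | 200 × 0.02 = 4 | 4 × 0.5 = 2 (1%) | 0 (0%) |
| 10% | 200 × 0.10 = 20 | 20 × 0.5 = 10 (5%) | 0 (0%) |

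The table shows how the rule would act; it is not an estimate of the bias.

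**The case against.** The strongest reply is that a sensible reader would not apply 5.1 literally. The explanation of unexpected is attached to the REC test, and 5.1 does not refer to it. Appendix 4 names the events as SAEs, and 5.2 has SAEs recorded before any filter on expectedness. On that reading the listed events are SAEs and nothing is lost.

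This stands as far as it goes: under-counting is a risk, not a settled result. It does not remove the conflict, because the instruction to record SAEs relies on a definition found only in 5.1.

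A reader might also infer more than the documents support:
- **That the device-SAE rate would fall to about zero whatever the truth.** Unlisted serious events count even on the literal reading, and the medical-judgement paragraph admits others.
- **That the morbidity part of primary objective 2 would count only unlisted events.** Nothing ties that objective to the SAE definition. Section 2.2 Outcomes expresses morbidity and mortality as percentages of the cohort, and section 7.2 collects mortality, readmission, further procedures and length of stay independently of SAE status.
- **That listed complications would escape all safety reporting.** The route for CAVT-related AEs to the manufacturer and the MHRA has no condition on expectedness. Only the 24-hour notification and the independent review are exposed.
- **That the sentence on deaths from pre-existing conditions excludes deaths from the index PE.** That is one possible reading. The sentence does not say, and it limits SAE reporting, not the collection of deaths.

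**Conclusion.** The point holds as an internal contradiction with a practical consequence. The protocol's only SAE definition conflicts with its own list of expected SAEs and with the way 5.2 uses expectedness. If followed literally it would misclassify serious listed events, bias secondary objective 12 downwards and divert those events from 24-hour notification and independent review.

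The conclusion rests on carrying the 5.2 meaning of unexpected into 5.1. The size of any under-count cannot be derived, because it depends on the true SAE rate, the share of events that are listed, and how many sites read 5.1 literally. The documents give none of these.

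The wording on pre-existing conditions is a smaller, separate ambiguity: the PE precedes the procedure, and 5.2 does not say whether it counts as pre-existing.

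**What to change.** 1. In 5.1, delete *and unexpected* from the SAE definition, so that an event is an SAE on seriousness alone.
2. In 5.2, keep expectedness, judged against Appendices 3 and 4, solely as the filter for REC reporting.
3. State in 5.2 whether the index PE is a pre-existing condition for the sentence on deaths. Reconcile this with the rule in the same section that only CAVT-related SAEs enter the 24-hour route, so that no new expedited duty arises by implication.

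Make these changes before sites begin to classify events. The cost is a few words of protocol text and some more SAE forms. Their number cannot be derived from the protocol, but the 24-hour route stays limited to CAVT-related SAEs.

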5.2 REPORTING PROCEDURES

At each data collection (30 days, 90 days and 6 months from the thrombectomy) the investigator will determine whether adverse events about the device and procedure have occurred. Subjects participating in the study should be encouraged to report these AEs spontaneously or in response to general, non-directed questioning.

Relevant events will be collected from the signing of informed consent to the completion of the follow up 6 months post index procedure.

19/10/25; V1.0

Adverse Events

AEs will be recorded for the CAVT and relevant procedure only.

Any AEs related to the CAVT will also be reported to the company Penumbra and MHRA.

Please find in Appendix 3 expected adverse events of CAVT and relevant procedure.

Serious Adverse Events

Death due to any pre-existing conditions will not be reported as SAEs.

Serious adverse events will be recorded.

Only CAVT related SAEs will be reported to the Principle Investigator, the Chief Investigator and Sponsor within 24 hours of being aware of the event. An Independent Medical Reviewer for the SAEs will also be appointed and the opinion will be recorded along with the PI / CI opinion. A SAE form should be completed.

All CAVT related SAEs should be reported to the Name of REC and copied to the Sponsor, and Penumbra where in the opinion of the Chief / Principal Investigator and the Independent Medical Reviewer, the event was:

- 'related', i.e. resulted from the administration of any of the research procedures; and
- 'unexpected', i.e. an event that is not listed in the protocol as an expected occurrence

Reports of related and unexpected SAEs should be submitted within 15 days of the Chief / Principal Investigator becoming aware of the event, using the Non-CTIMP safety report to REC form for non-IMP studies.

Sponsor contact details for reporting SAEs

Please send SAE forms to: R&D Governance / R&D Office

[contact] (Mon to Fri 09.00 – 17.00)

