2 STUDY OBJECTIVES

2.1 PRIMARY OBJECTIVES

- 1. To evaluate the effectiveness of PE CAVT as a treatment for intermediate and high-risk PE as measured by change pulmonary arterial pressure and in RV/LV (Right Ventricle to Left Ventricle diameter) ratio at 48 (- 24 / + 48) hours post procedure.
- 2. Ascertain the mortality and morbidity profile for CAVT within intermediate and high-risk PE, within 48 (± 12) hours post procedure, 30 (± 7) days, 90 (± 14) days and 6 months (+/- 30 days).

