2.2 OUTCOMES

Effectiveness of CAVT will be determined by the change in RV/LV ratio on Echocardiography and the reduction in direct invasive measurement of the Pulmonary artery pressure at the beginning and end of the procedure.

Technical success will be determined by the operator comparing pre and post imaging and pulmonary artery pressures. Morbidity and mortality will be expressed as percentage of the cohort. Imaging features, service design, PERT team decision and comorbidities effect on outcomes will be assessed via regression analysis.

The service design and effect on thrombectomy will be assess by service questionnaire at site set up describing the service design factors. Patient reported outcomes like quality of life and breathlessness will be assessed to determine improvement as per their validated questionnaires.

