4.2 RECRUITMENT

Patients will be assessed for inclusion into the study by the research nursing team or trained member of the PERT team at point of referral to the local PERT team. Consent for inclusion in the data recording can be sought retrospectively in an out of hours setting, up to 96 hours post referral. All patients referred with an intermediate or high-risk PE (according to ESC guidelines (1)) will be included (after consent) into the wider dataset, with more specific data collected on those undergoing CAVT treatment.

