4.3 CONSENT

Consent for inclusion into the trial dataset will be obtained by the research nurse or PERT team, only after a full explanation has been given, an information leaflet offered, and time allowed for consideration. Consent can be sought up to 96 hours after the referral to the PERT to allow for out of hours setting. No study specific data will be collected before a consent form is signed. The right of the participant to refuse to participate without giving reasons must be respected. There will be no change in the patients' treatment pathway. Patients will be able to withdraw from the study at any point. If a patient loses capacity, no further information will be obtained but their data already included will not be deleted. Patients who are unable to consent will be able to be included if a appropriate proxy consent is available. Patients who die within the 96 hours will also be able to be included if appropriate proxy consent available.

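### Section 5.2 opens event collection at consent, which may follow the CAVT procedure by days; as written, this biases 48-hour morbidity and device-related SAE incidence downward for late-consented CAVT participants

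*Protocol*

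**What the plan says.** **Event window.** Protocol section 5.2: "Relevant events will be collected from the signing of informed consent to the completion of the follow up 6 months post index procedure". On scope, the same section says: "AEs will be recorded for the CAVT and relevant procedure only". It has the investigator determine device and procedure events at 30 days, 90 days and 6 months.

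**Timing of consent.** Section 4.2: "Consent for inclusion in the data recording can be sought retrospectively in an out of hours setting, up to 96 hours post referral". Section 4.3 repeats the limit ("Consent can be sought up to 96 hours after the referral to the PERT to allow for out of hours setting") and adds: "No study specific data will be collected before a consent form is signed". It also admits patients who die within the 96 hours, if proxy consent is available. Neither section requires a CAVT patient to consent before the procedure.

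**What is to be estimated.** Primary objective 2 in section 2.1 begins: "Ascertain the mortality and morbidity profile for CAVT within intermediate and high-risk PE, within 48 (± 12) hours post procedure". It goes on to 30 days, 90 days and 6 months. Secondary objective 12 is the incidence of device-related SAEs. Under Outcomes: "Morbidity and mortality will be expressed as percentage of the cohort".

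**The concern.** The first time point of primary objective 2 covers the hours directly after the procedure. The event window in 5.2 is tied to a different clock, the signature on the consent form, which may come after the procedure and even after the whole 48-hour period. A perforation, access-site bleed or arrest during a procedure that precedes consent then falls outside the window.

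Morbidity is a percentage of the cohort. A late-consented participant stays in the denominator while events before signature leave the numerator, so the error goes one way, downward. It can also differ between hospitals whose consent timing differs, which would blur the between-hospital comparison in secondary objective 6. No later analysis can restore events that sites were told not to collect, so this has to be settled in the protocol.

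**Working it through.** The protocol gives no complication rate and no share of late consents, so there is no stated figure to reproduce. Two checks were made.

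**1. How much of the 48-hour period can precede consent?**

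Inputs: latest consent 96 h after referral (4.2, 4.3); morbidity period 48 h after the procedure (2.1); procedure t hours after referral (t not stated, so varied). With consent at the limit, the uncovered share is min(1, (96 − t)/48).

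| Procedure, hours after referral | Consent, hours after procedure | Share of 48 h before consent |
|---|---|---|
| 0 | 96 | 100% |
| 24 | 72 | 100% |
| 48 | 48 | 100% |
| 72 | 24 | 50% |
| 96 | 0 | 0% |

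At the outer tolerance of 48 + 12 = 60 h, a procedure up to 36 h after referral (96 − 60) is still wholly uncovered. At t = 48 the uncovered share is 48/60 = 80%. These are worst cases, since consent at 96 h is the limit and not the norm.

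**2. What does this do to the recorded rate?**

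Let p be the true 48-hour complication rate, q the share of CAVT participants consented after the procedure, and s the share of their 48-hour events that precede consent. If early and late consenters have the same risk,

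recorded rate = p × (1 − q × s).

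All three values are assumptions. For p = 5%, which is 10 of the planned 200 thrombectomy patients:

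| q | s | 1 − q × s | Recorded rate | Expected patients recorded, of 200 |
|---|---|---|---|---|
| 0.25 | 0.5 | 0.875 | 4.4% | 8.8 |
| 0.25 | 1 | 0.75 | 3.75% | 7.5 |
| 0.5 | 1 | 0.5 | 2.5% | 5.0 |
| 0.75 | 1 | 0.25 | 1.25% | 2.5 |

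The relative under-count is q × s. For q from 0.10 to 0.75 and s from 0.5 to 1 it runs from 0.10 × 0.5 = 5% to 0.75 × 1 = 75%. It is zero if every CAVT participant consents before the procedure, or if sites collect pre-consent events despite 5.2. If risk differs between early and late consenters, q must be read as the share of all 48-hour events that arise in late consenters.

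**3. Is there another source for the missing events?**

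Section 7.2 lists, for CAVT patients, procedural success and outcome, further procedures, IVC filter insertion, and observations and biochemistry on the days after the procedure. The CAVT table in Appendix 1 has a procedure-outcome row but no adverse-event row. Some complications would leave a trace in these items, but none of them is a dedicated complication field.

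**The case against.** The best case for the protocol is that a look-back was intended. Consent for data recording may be retrospective, and late-consented patients still need admission observations, PERT decisions and start and finish pulmonary artery pressures, all of which can predate signature. Including a patient who died before proxy consent makes sense only if earlier data can be abstracted. On this view the bar in 4.3 governs when staff may collect, not which past events count. The reviews in 5.2 are framed by cause (device and procedure), and Appendices 3 and 4 list plainly procedural events. Late consent is also tied to out-of-hours working, with assessment at referral as the norm.

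Much of this stands. It shows that abstraction of earlier data is not forbidden, and that the protocol wants procedural events. It does not remove the sentence in 5.2 that starts events at signature, and 12 sites could apply that sentence differently.

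Three stronger readings are tempting, and the documents do not support them:

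- **All early complications are lost.** Only CAVT participants consented after the procedure are affected, and only for events before signature.
- **Nothing else would catch these events.** The 30-day review, the procedure-outcome item and the further-procedures item may recover some. Section 7.2 also presents its list as sample data points, so a field not shown there may exist.
- **Late-consented patients are the sicker ones.** This is plausible, but no section says so.

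**Conclusion.** The point holds as a conflict between 5.2 and the consent rules in 4.2 and 4.3. Followed literally, 5.2 drops procedural and early complications for CAVT participants consented after the procedure, and biases 48-hour morbidity and device-related SAE incidence downward. The direction follows from the text. The size does not: it depends on p, q and s, none of which is stated, and the 5% to 75% relative under-count above only spans assumed values.

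Mortality is largely unaffected, because it is a separate data item at discharge and at each follow-up, and early deaths can enter by proxy consent. In such a case the death would be counted, while a complication behind it could fall outside the event window. The paired analysis of change in LV/RV ratio is not touched.

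A look-back may have been meant. If so, the wording of 5.2 says otherwise and should be corrected before sites rely on it.

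**What to change.** 1. Reword the window in 5.2, for example: *For CAVT participants, device and procedure adverse events are collected from the start of the CAVT procedure to 6 months, whatever the date of consent. Events before consent are abstracted from the clinical record once consent or proxy consent is in place.*
2. State in 4.3 that consent, once given, covers data back to PERT referral, so that the bar on collection before signature is understood as a rule on when staff may collect. Align the consent wording with this.
3. Add an adverse-event row at Day 2 and Discharge to the CAVT table in Appendix 1, so that the 48-hour time point has its own ascertainment.

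With the first change the uncovered share is zero and the window no longer lowers the recorded rate. The cost is protocol and consent wording plus minor extra chart abstraction by research nurses who already retrieve the Day 1 to Day 5 data. The recorded event rate will be somewhat higher, as it should be. No treatment or care pathway changes.

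### Section 5.2 does not send SAEs judged unrelated to CAVT, or deaths put down to pre-existing conditions, to the independent reviewer, so missed device attributions may go uncorrected

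*Protocol*

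**What the plan says.** Protocol section 5.2 sets these rules:

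- **Recording.** "Serious adverse events will be recorded". This sentence has no relatedness limit, whereas recording of non-serious AEs is limited to CAVT and the relevant procedure.
- **Reporting.** "Only CAVT related SAEs will be reported to the Principle Investigator, the Chief Investigator and Sponsor within 24 hours".
- **Deaths.** "Death due to any pre-existing conditions will not be reported as SAEs". The section does not say who makes this attribution or by what criterion.
- **Independent review.** An Independent Medical Reviewer is to be appointed for the SAEs, and that opinion is recorded beside the PI/CI opinion. Which SAEs the reviewer receives is not stated.
- **Onward reports to the REC and Penumbra.** These start from CAVT-related SAEs. The investigator and the reviewer must both hold that the event was related and unexpected. Related means that it "resulted from the administration of any of the research procedures".
- **A separate route.** Any AE related to CAVT also goes to Penumbra and the MHRA, with no two-opinion condition.

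Elsewhere, section 5.1 lists "Results in death" among the SAE criteria, and Appendix 4 names death as an expected SAE. Section 4.3 says "There will be no change in the patients' treatment pathway", and section 6.2 says that the decision to treat is not protocolised. Secondary objective 12 is the incidence of device-related SAEs. Section 7.2 collects mortality for all patients at discharge and at each follow-up, with all-cause and PE-related mortality named at 30 days and 6 months.

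**The concern.** Whether an SAE belongs to the device or to the disease is a central safety question for CAVT, and the first answer comes from the site investigator. Section 8.4 says that the device manufacturer funds the database, set-up and data collection, so an independent opinion on attribution is a sensible safeguard. It works fully only if the reviewer can see the events in which a device contribution might have been missed. Those are the SAEs that the site called unrelated and the deaths that it put down to the underlying disease, and 5.2 sends neither group to the reviewer.

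Secondary objective 12 is most exposed, together with the serious part of the morbidity profile in primary objective 2. The mortality count itself is not at risk. What lacks a review process is the division of deaths between disease and device. A later analysis plan cannot repair this, because it cannot recover opinions that were never sought.

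**Working it through.** The protocol gives no SAE rate or attribution accuracy, so there is no figure to reproduce. The check is mainly one of text and logic.

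**1. Where each kind of event goes (5.2 and 7.2, CAVT participants)**

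| Event | Recorded | Reported to PI, CI and sponsor | Sent to the reviewer |
|---|---|---|---|
| SAE judged CAVT related | Yes | Yes, within 24 hours | Yes, on a natural reading |
| SAE judged unrelated | Yes | No | Not stated |
| Death put down to a pre-existing condition | In the mortality data; as an SAE, unclear | Not as an SAE | Not stated |

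**2. Consequence for objective 12.** Let S be the SAEs that the site calls related and R those that the reviewer calls related.

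- If the reviewer receives only S, then R lies inside S and the reviewed count cannot exceed the site count.
- If the reviewer receives every recorded SAE, R can contain events outside S and the reviewed count can be higher.

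The protocol does not say which applies, or whether objective 12 is counted from S, from R or from both.

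**3. Consequence for REC reports.** The rule starts from CAVT-related SAEs and needs both opinions, so the reportable set is at most the overlap of S and R. The reviewer can veto a report but cannot add one. This holds under either reading of step 2.

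**4. Definition of related.** The REC rule ties relatedness to research procedures. Sections 4.3 and 6.2 make CAVT part of usual care, chosen outside the protocol. The definition therefore does not name the exposure of interest.

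**5. The death exemption.** The index PE precedes every CAVT, so it is arguably a pre-existing condition in every treated patient. Section 1.4 also says that patients with cancer are included. A death from right heart failure after an unsuccessful thrombectomy could be put down to the PE and left out of SAE reporting. Section 5.1, taken alone, would make death an SAE criterion.

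**6. Illustration only.** The planned 200 CAVT patients come from the protocol; every rate is assumed and errors are taken as independent. Let p be the true device-related SAE rate, q the rate of other SAEs and s the site's sensitivity (0.7 to 0.9). Site specificity, reviewer sensitivity and reviewer specificity are each 0.95.

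- Site count = 200 × (p·s + q·0.05)
- Reviewer sees only S and both must agree = 200 × (p·s·0.95 + q·0.05·0.05)
- Reviewer sees all and the reviewer's opinion counts = 200 × (p·0.95 + q·0.05)
- Reviewer sees all and either opinion counts = 200 × (p·[1 − (1 − s)·0.05] + q·[1 − 0.95²])

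For p = 2%, q = 10%, s = 0.7, the four counts are:

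- 200 × (0.014 + 0.005) = 3.8
- 200 × (0.0133 + 0.00025) = 2.7
- 200 × (0.019 + 0.005) = 4.8
- 200 × (0.0197 + 0.00975) = 5.9

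| p, q | True | Site | Only S, both agree | All, reviewer's opinion | All, either opinion |
|---|---|---|---|---|---|
| 2%, 10% | 4.0 | 3.8–4.6 | 2.7–3.5 | 4.8 | 5.9 |
| 5%, 15% | 10.0 | 8.5–10.5 | 6.7–8.6 | 11.0 | 12.8–12.9 |

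Under these assumptions, one-way review falls below the true count, full review lies somewhat above it, and an either-opinion rule overshoots further because false positives add up.

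**The case against.** The strongest reply is that 5.2 restricts reporting, not recording. SAEs are recorded whatever their cause, and the limit to CAVT-related events governs 24-hour reporting. The reviewer is appointed for the SAEs without restriction. Nothing lets the reviewer's opinion overwrite the investigator's, and nothing ties objective 12 to the reported set. The two-opinion rule governs onward reporting; it is not an outcome definition.

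Most of this stands, and it rules out several stronger conclusions that a reader might draw:

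- *Sites remove SAEs from the data.* The recording sentence says otherwise.
- *Review can only ever lower the objective 12 count.* This needs the reviewer to see only the reported set and the reviewed set to be counted. The protocol states neither. If the investigator's classification is counted, review does not move the count at all.
- *Every death in a CAVT or cancer patient is exempt.* The death must be due to the pre-existing condition. Having the condition is not enough, and a death from cardiac perforation in a patient with cancer would not qualify.
- *Sections 5.1 and 5.2 flatly contradict each other.* Section 5.1 defines an SAE as untoward and unexpected, so a reporting exemption for deaths from underlying disease can be squared with it. There is tension because the exemption is undefined.
- *No CAVT event can ever be reported.* The REC sentence is about CAVT-related SAEs, so its intent can be understood. CAVT-related AEs also reach Penumbra and the MHRA by the separate route.

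The reply does not supply a sentence that gives the reviewer the unrelated SAEs or the exempted deaths, a statement on whether the index PE is pre-existing, or a rule for disagreement. Nor does it change the one-way direction of REC reports.

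**Conclusion.** The point holds in conditional form and should be acted on. It is certain that SAE reporting depends on a prior judgement of relatedness, that the death exemption has no criterion or named attributor, and that for REC reports the reviewer can veto but not add. It is conditional that review cannot correct missed device attributions for objective 12: this follows if the reviewer receives only the reported SAEs, which is the natural reading of the order of sentences but is not stated.

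No size of bias can be derived from the documents. The counts above show direction under assumed rates and are not estimates for this study. All-cause mortality is unaffected, and PE-related mortality is collected separately.

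**What to change.** In section 5.2, for CAVT participants:

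- (a) remove the exemption for deaths due to pre-existing conditions;
- (b) send every recorded SAE and every death, with the site's relatedness opinion, to the planned Independent Medical Reviewer;
- (c) define related as resulting from the CAVT device or procedure;
- (d) state that objective 12 is reported twice, by the investigator's and by the reviewer's classification.

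Item (d) shows disagreement openly. An either-opinion rule is not recommended, because it trades missed events for false positives.

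The change is one of wording and leaves patient care untouched. It costs more SAE forms for the reviewer, in about 200 patients, and possibly a slightly higher device-related SAE rate.
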